TABLE 5. Probability of detecting a "promising" effect

LIST OF FIGURES

FIGURE 1. ESR1 Mutations are associated with poor outcome

FIGURE 2. Drug Response in ESR1 wildtype and mutant cells, and context dependent gain-of-function of mutant ER in genome-edited cells.

FIGURE 3. Detection of ESR1 mutation in liver metastasis and plasma

FIGURE 4. Study Schema

LIST OF ABBREVIATIONS AND DEFINITION OF TERMS

The following abbreviations and special terms are used in this study Clinical Study Protocol.

TABLE 1. List of abbreviations

Abbreviation or special term	Explanation
AE	Adverse events
AI	Aromatase Inhibitor
CR	Complete response
CRS	Clinical research services
CTCAE	Common terminology criteria for adverse events
ctDNA	Circulating Tumor DNA
ddPCR	Droplet digital PCR
DMC	Data monitoring committee
DSMC	Data safety monitoring committee
eCFR	Electronic case report forms
ER+	Estrogen Receptor Positive
ESR1	Estrogen Receptor 1
ESR1-mt	Estrogen Receptor 1 mutant
ESR1-wt	Estrogen Receptor 1 wild type
FDA	Food and Drug Administration
GDP	Good clinical practice

Abbreviation or special term	Explanation
ICH	International clinical research
IRB	Institutional review board
ISS	Investigator sponsored study
LBD	Ligand binding-domain
MBC	Metastatic Breast Cancer
OS	Overall Survival
PD	Progressive disease
PFS	Progression Free Survival
PR	Partial response
PR	Progesterone receptor
RR	Response rate
SAE	Serious adverse events
SD	Stable disease
SRM	Study reference manual
TAM	Tamoxifen
TTP	Time to progression

1. INTRODUCTION

[figure not shown]
1.1 Background

A major challenge is to identify the drivers of progression from primary to metastatic breast cancer, and identify new targets for treatment. Mutations in the estrogen receptor (ESR1) are a potential resistance mechanism to endocrine therapy (1-9). In cell based-models, the presence of a mutation in ESR1 confers constitutive and ligand independent activity.(3) Although these mutations are extremely rare in previously untreated patients with early breast cancer, the development of these mutations over time after exposure to hormonal therapy with tamoxifen or AIs has been recently demonstrated to occur in as many as 14-54% of patients with estrogen receptor- positive (ER+) metastatic breast cancer (MBC).(7)

The mutations primarily occur in the ligand binding domain (LBD) of ESR-1 and there have been at least 6 mutations described. A recent study by Chandarlapathy identified additional (albeit very rare) ESR1 mutations (10) Patients whose tumors harbor *ESR1* mutations have poor overall survival. In a recent large meta-analysis including data from 1540 patients, 28% had ESR mutations and had significantly worse PFS. The presence of ESR1 mutation, however, did not predict outcome on fulvestrant based therapy. (11) Even using a small cohort of patients, we reported shorter progression free survival (PFS) in patients with endocrine-resistant ER+ breast cancer receiving palbociclib who had *ESR1* mutations detected in cfDNA (12)

Together these observations support the tenable hypothesis that these mutations are clinically significant and the tumors that harbor them are strongly dependent upon ESR1 signaling.

Interestingly, in vitro, both tamoxifen and fulvestrant appear to have activity in the setting of ESR1 mutations; although different ESR1 mutations appear to have varying thresholds for effective dosing of both agents that define their level of partial resistance (3). Our group has recently performed detailed analysis of drug response in genome-edited T47D and MCF-7 cells, and these data were published Bahreini et al (13) Briefly, we introduced the most

frequent ESR1 hotspot mutations D538G and Y537S, and observed not only ligand-independent activity of the mutant ER in growth and transcriptional activity assays, but also observed antiestrogen resistance: cells with mutant ER had higher IC50 for the SERMs 4OHT and raloxifene, and the SERDs fulvestrant and AZD9496 compared to WT (Figure 2A). We did observe differences between the mutants, with Y537S displaying increased resistance compared to D538G.

Figure 2: A) ESR1 mutant-cells display resistance against selective estrogen receptor modulators (SERMs) and selective estrogen receptor degraders (SERDs). Graphical (a) and tabular (b) presentation of half maximal inhibitory concentration (IC50) values that were determined in dose–response curves in wild-type (WT),

Y537S and D538G cells treated with 20 pM estradiol (E2) plus varying doses of 4OHT, raloxifene (Ral), fulvestrant (Ful), and AZD9496 in T47D and MCF7 cell lines. One-way analysis of variance was performed to compare the IC50 values of mutants to WT within each cell line and drug (*p < 0.05, **p < 0.01). (13).

Of note, our recent unpublished data shows metastatic properties of the D538G mutant receptor which might explain high MAF of this hotspot mutation despite decreased resistance compared to Y537S. We hypothesize that these novel gain-of-function activities are related to target genes specifically regulated by mutant ER (Figure 2B).

[figure not shown]

Figure 2B: Genome-wide transcriptomic analysis reveals regulation of ligand-independent estrogen receptor (ER) targets, and of novel target genes by ER α mutants in T47D and MCF7 cells. T47D and MCF7 cell lines were hormone-deprived for 3 days, treated with vehicle (veh) or 1 nM of estradiol (E2) for 24 h, RNA was isolated and RNA sequencing analysis was performed. The heat map shows normalized log₂ fold change (FC) of genes differentially regulated in mutants vs wild-type (WT) in the absence of ligand (FC >2, p value <0.005). The genes are sorted based on E2 regulation in WT (red arrow ligand-independent E2 activated genes, blue arrow ligand-independent E2 downregulated genes, green circle ligand-independent non-E2 regulated genes, i.e. “novel target genes”). (13).

As our studies indicate, the effect of different ESR1 mutations and their response to therapy are cell and context dependent. Thus it is important to determine the clinical relevance of these mutations and the efficacy of tamoxifen and fulvestrant in the setting of AI resistance especially since these two drugs possess distinct modes-of-action.

Specifically, as mutations in ESR1 appear to constitutively activate the receptor, the intrinsic ability of fulvestrant (in contrast to tamoxifen) to facilitate ER degradation may provide a mechanism to circumvent AI resistance with a more durable response. Our lab has recently published two publications on this important topic (17, 18).

Both fulvestrant and tamoxifen are standard hormonal therapies in patients with AI resistance. In a prospective setting, the efficacy and potential resistance of these agents in ESR1-mt tumors is unknown. There is some evidence that Fulvestrant treatment has efficacy in the tumors with ESR1 mutations, but this is less known for Tamoxifen. The prevalence of ESR1-

mt in the metastatic breast cancer population has been reported to be 15-50%. Some of these patients were heavily pre-treated endocrine- refractory patients. There is some but limited information on the prevalence of ESR1 mutations after AI failure and the incidence of ESR1 mutation as an effect of subsequent endocrine therapies. It is important to ascertain the prevalence of ESR1-mutations in patients earlier in their metastatic disease course, which is the time in which agents such as tamoxifen and fulvestrant are typically used. It is critical, therefore, to identify biomarkers in patient subsets that are predictive of rationale combinations of hormonal therapies as strategies to combat endocrine resistance from the outset.

Many patients now receive palbociclib with an AI in the first-line metastatic setting. ER-positive luminal breast cancer is particularly dependent on the interaction of cyclin Ds with the protein complexes CDK4 and CDK6 to drive cellular proliferation(18, 19). Together, they facilitate phosphorylation/inactivation of the Retinoblastoma tumor suppressor protein (RB), and this leads to progression through the G1 restriction point to the S phase of the cell cycle and, thus, cellular proliferation. Loss of RB is a potential mechanism of resistance to CDK4/6 inhibitors in vitro, but this needs to be validated in patients. Palbociclib (Ibrance, Pfizer) is an oral small molecule inhibitor of CDK4 and CDK6. Palbociclib received accelerated FDA approval based on the results of PALOMA-1, a randomized Phase 2 study comparing palbociclib plus letrozole versus letrozole alone in women with ER-positive HER-2-negative advanced breast cancer. PALOMA-1 showed significantly longer PFS with palbociclib plus letrozole (20.2 months) than with letrozole alone (10.2 months) (20)

The PALOMA-2 trial was designed as a confirmatory study and was a double-blind, randomized, Phase 3 2:1 comparison of palbociclib plus letrozole versus placebo plus letrozole. The median progression free survival was 24.8 months with the combination compared to 14.5 months in the placebo-letrozole group. The most common grade 3 or 4 adverse events were neutropenia, leukopenia, and fatigue (21).

The PALOMA-3 trial was a randomized, double-blind, placebo-controlled phase 3 trial comparing palbociclib plus fulvestrant compared with placebo plus fulvestrant in women with hormone receptor positive HER-2 negative metastatic breast cancer after progression on prior endocrine therapy. The median PFS on palbociclib plus fulvestrant was about 11 months, and it was not different in patients with greater than or equal to grade 3 neutropenia versus those who did not (22).

However, there is significant need for predictive biomarker development to guide therapy in patients who are resistant to AIs and/or have received prior palbociclib. Loss of RB is one potential biomarker of CDK4/6 resistance, but it is actually not commonly described in ER-positive breast cancer. Other potential biomarkers include CCnE1, amplification of E2F, cyclin E levels, or loss of CDKN1A, that has been linked to tamoxifen resistance.

In addition, there is currently no data to support CDK4/6 beyond progression in patients with AI-resistant disease. It is unknown whether these agents can prevent emergence of resistance in patients formerly treated with an AI/CDK4/6 combination. It is also unknown whether they could circumvent the ligand-independent activation of ER signaling that occurs in the setting of an ESR1 mutation. Limited ongoing studies seek to address this question. The BioPER trial (NCT013184090) is an open label non-controlled phase II trial assessing Palbociclib in combination with endocrine therapy of investigators choice after prior successful treatment with a Palbociclib containing regimen, looking for molecular profiles identifying patient who may benefit from continued Palbociclib in this setting. This trial focuses on Rb status and related signaling as potential biomarkers.

A second study of Palbociclib after CDK and endocrine therapy (PACE) (NCT03147287) is examining Fulvestrant, Palbociclib and Avelumab for patients with metastatic disease. This trial is not estimated to be completed until 2024. A third ongoing trial (NCT02738866), phase II trial of Palbociclib and Fulvestrant in patients with HR+ MBC who have progressed on treatment with Palbociclib and an AI. There are currently no trials examining the combination of Palbociclib with Tamoxifen vs Palbociclib with Fulvestrant in patients previously exposed to a CDK4/6 inhibitor.

The focus of this study will be examination of ESR1 mutations as a biomarker. Both tamoxifen and fulvestrant are possible standard-of-care therapies in this clinical setting. We will assess the detection of ESR1 mutations in plasma over time on both therapies.. Additionally, since testing for ESR1 is not fully standardized and because it is a clinically relevant question, we will collect response data as measured by PFS for fulvestrant plus palbociclib vs tamoxifen plus palbociclib for treatment of MBC, unselected by ESR1.

While previous studies have predominately evaluated for ESR1-mt in tumor tissues, use of novel technology to assess for ESR1-mt in plasma makes it clinically feasible to assess the variability of this marker over time in response to treatment. A PCR Sanger sequencing-based assay for detection of the five ESR1 mutations is available for solid tumor detection. A new next generation sequencing assay, MammaSeqSM, which measures all reported ESR1 mutations, and mutations and copy number alterations in another 77 genes commonly mutated in breast cancer, is also under development in the UPMC Molecular Pathology laboratory and will be incorporated into this protocol. We have recently published on the generation and use of MammaSeqSM (20) For detection of ESR1 mutations in plasma, a droplet digital PCR (ddPCR) assay is performed in the research laboratory of Drs. [name] PhD and [name]. Using this assay, we have identified ESR1 mutations in 5/30 (16.7%) of patients with metastatic breast cancer, and when only considering those with an ER-positive primary breast cancer, we find ESR1 mutations in 5/20 (25%) of patients. The MammaSeqSM capabilities would allow us to more comprehensively assess the initial presence and also the acquisition of mutations during treatment with tamoxifen plus palbociclib and fulvestrant plus palbociclib.

This may provide an additional means to discern differences between these two mechanistically distinct treatments and also enable us to target our analysis to more specifically determine the significance of ESR1 mutations per se as prognostic and predictive indicators.

1.2 Research hypothesis

1. In the 2nd to 3rd line of AI resistant WT ESR1 MBC, Fulvestrant plus palbociclib treatment will result in earlier detection of ESR1 mutations compared to treatment with tamoxifen plus palbociclib
2. In the 2nd to 3rd line of AI resistant mutant ESR1 MBC, Fulvestrant plus palbociclib will result in increased PFS compared with tamoxifen plus palbociclib
3. Change of allele frequency of ESR1 mutation is associated with PFS in all groups

1.2 Rationale for conducting this study

We propose a pilot clinical trial comparing the standard doses of fulvestrant plus palbociclib to tamoxifen plus palbociclib while evaluating subjects for the presence of ESR1 mutation. The goal is to obtain plasma, and tumor samples if available, that will look at the changes in time in the detection of ESR mutations while on non-AI therapy but with continued exposure to palbociclib. As both tamoxifen or faslodex would be standard next line options for patients progressing on AI, we would like to look at these two populations, This project will provide needed information regarding the prevalence of ESR1-mt in patients with ER+ MBC in the 2nd -3rd line setting when hormonal therapies are predominantly used. We will determine the presence of ESR1-mt by analyzing tumor biopsies and by making use of the novel technology of detection of ESR1-mt from circulating tumor DNA (ctDNA) by digital droplet PCR (ddPCR) in plasma. This technology allows the non-invasive detection and measurement of the level of circulating ESR1-mt over time and in response to treatment. Measuring ESR1 both in tissue and plasma will allow for determination of concordance between both sites, and may remove any bias that metastatic tumor heterogeneity could contribute. The tissues collected will also be assessed for other alterations in ESR1 such as amplifications or fusions, as well as assessment of ESR1 abnormalities on ER binding sites and whether this is altered after fulvestrant treatment. Our group has been able to demonstrate congruence between an ESR1 mutation found on liver biopsy and in plasma using ddPCR in a patient with ER+ MBC. (figure 4, unpublished and reference 23).

FIGURE 3. Detection of ESR1 mutation in liver metastasis and plasma

[figure not shown]

Figure 3: Detection of mutant ESR1D538G in a liver biopsy and circulating tumor (ct) DNA. A) Representative droplet digital PCR (ddPCR) using ~20ng of DNA isolated from a liver biopsy of metastatic breast cancer. B) Mutant ESR1D538G mutant allele frequency (mutant/wt alleles) in a liver biopsy of metastatic breast cancer and associated ctDNA. For ctDNA analysis 40ml of blood was collected in Streck tubes, plasma separated, DNA isolated and ddPCR performed using ~20ng of DNA.

This proposal will provide a prospective pilot study of the effect of the presence or absence of ESR1-mt on response to a commonly used therapy in the metastatic setting. This study will provide important data regarding a potentially very common and clinically relevant mutation that likely effects response to frequently used treatments. The results obtained can then be used as springboard to assess other potential therapies in this setting and to further study the biologic relevance of the mutation.

1.3 Benefit/risk and ethical assessment

This study will be conducted in accordance with the ethical principles that have their origin in the current Declaration of Helsinki and will be consistent with applicable US regulatory requirements and International Conference on Harmonization Good Clinical Practice (ICH GCP).

The study will be conducted in compliance with the protocol. The protocol and any amendments and the patient informed consent will receive Institutional Review Board (IRB) approval prior to initiation of the study.

Study personnel involved in conducting this trial will be qualified by education, training, and experience to perform their respective task(s). This trial will not use the services of investigators or study personnel where sanctions have been invoked or where there has been scientific misconduct or fraud (e.g., loss of medical licensure, debarment). Investigators are responsible for the conduct of the study at their study site.

2. STUDY OBJECTIVES

2.1 Primary objective

1. Assessment of longitudinal changes in allele frequency of ESR1 mutation in plasma in patients treated with Fulvestrant plus palbociclib compared to tamoxifen plus palbociclib
2. Assessment of genomic alterations (using MammaSeq) associated with wildtype or mutant ESR1
3. Assessment of the functionality of ESR1 in tumor biopsies collected prior to and following treatment with fulvestrant plus palbociclib, or tamoxifen plus palbociclib, as assessed by RNAseq
4. Safety and toxicity assessment

2.2 Secondary objectives

1. Collection of clinical outcome data in this limited patient population
 - a. Progression free survival (PFS), Objective response rate (ORR) and Clinical benefit rate (defined as CR+PR+ stable disease at any tumor assessment) and clinical benefit rate at 6 months (CBR6) (defined as CR+PR+ stable disease for at least 6 months) in the entire cohort, and the ESR1-mt cohorts
2. Correlation between longitudinal changes in circulating levels of ESR1 mutations and clinical outcome
3. Assessment of concordance of ESR1 status in plasma and biopsy samples
4. Use of cfRNA to determine gene expression in AI resistant mutant ESR1 MBC

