ESR1 mutation will be analyzed both from tumor biopsies and peripheral blood circulating tumor DNA. These tumor biopsies and peripheral blood circulating tumor DNA will be assessed for the following most commonly described ESR1 mutations using Sanger sequencing of the three ESR1 exons which will assess for 23 different ESR1 mutations including the 6 most commonly described (S463P, L536Q, Y537S, Y537C, Y537N, and D538G). Next generation sequencing (NGS) and/or digital droplet PCR (ddPCR) of blood and tumor specimens will also be performed to look at co-existent mutations. It will then be reported as the frequency of occurrence of ESR1 mutation in the cohort of enrolled patients as well as in the cohort of patients treated with fulvestrant plus palbociclib and tamoxifen plus palbociclib.

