12.1 Statistical analysis plan

The primary analysis will be conducted at least 6 months after the last patient is enrolled. Cox proportional hazards regression will be used to estimate hazard ratios comparing PFS for tamoxifen plus palbociclib and fulvestrant plus palbociclib. Fulvestrant will be considered promising for the unselected population if the fitted hazard ratio is < 0.8 , and for the ESR1-mut subpopulation if the hazard ratio is < 0.65 .

Response rate will be compared between treatment arms using the mid-P correction to Fisher's exact test for univariate comparisons, and logistic regression for exploratory multivariable models. Cox proportional hazards regression will be used for analyses with overall survival as the endpoint.

Adverse events will be reported for all patients in the safety cohort defined above, summarized by treatment group. Adverse events and serious adverse events will be tabulated in order of prevalence, with the highest grade reported by each patient.

Concordance of ESR1 status in plasma and biopsy samples will be assessed primarily by agreement regarding presence/absence of mutations for tissue and blood samples collected no more than 30 days apart and without intervening therapy. Kappa statistics adjusted for clustering (both pre-therapy and post-therapy time points for some subjects) will describe basic agreement. Additionally, between-subject and within-subject variation in mutant allele frequency will be compared using linear mixed models and the concordance correlation coefficient. This approach (complementary **analysis of categorical and continuous versions of**

ESR1 mutation status) may also be applied to assessment of within-patient longitudinal change. The primary analysis for these correlative studies will examine presence and allele frequency of any ESR1 mutation. Secondary analyses will examine and compare tissue-blood concordance and longitudinal change in liquid biopsy measures for specific ESR1 mutations. Level and change in circulating levels of ESR1-mt will be assessed as predictors of PFS using Cox proportional hazards regression with time-varying covariates. All hypothesis tests will be two-sided.

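### Section 12.1's additional concordance correlation on tissue and plasma allele frequency cannot separate dilution of tumor DNA from discordance; the primary kappa analysis is sound and should stay

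*Combined protocol and SAP*

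**What the plan says.** Section 2.2 lists the "Assessment of concordance of ESR1 status in plasma and biopsy samples" as secondary objective 3 and names no statistic. Section 1.2 (Rationale for conducting this study) gives the purpose: "Measuring ESR1 both in tissue and plasma will allow for determination of concordance between both sites". Section 6.3.5 adds that comparing plasma with tumor should also help to assess heterogeneity between plasma and a particular metastatic site.

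The method is in 12.1 and has two layers.

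- **Primary layer, categorical.** "Concordance of ESR1 status in plasma and biopsy samples will be assessed primarily by agreement regarding presence/absence of mutations", on tissue and blood taken no more than 30 days apart with no therapy in between. "Kappa statistics adjusted for clustering (both pre-therapy and post-therapy time points for some subjects) will describe basic agreement".
- **Additional layer, continuous.** In the same paragraph, "between-subject and within-subject variation in mutant allele frequency will be compared using linear mixed models and the concordance correlation coefficient". No transformation, normalisation or handling of wild-type pairs is stated.

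Section 12.1 also says: "The primary analysis for these correlative studies will examine presence and allele frequency of any ESR1 mutation". The continuous layer is therefore more than a footnote. The only definition of allele frequency is in the Figure 3 legend, which speaks of "mutant allele frequency (mutant/wt alleles) in a liver biopsy of metastatic breast cancer and associated ctDNA". It has no term for biopsy purity or for the tumor share of plasma DNA.

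**The concern.** The CCC measures departure from the line of identity, so it falls whenever two measurements differ in mean or scale, even if one is an exact multiple of the other. Tissue and plasma allele frequencies have no reason to be equal. The first is the clonal share diluted by normal cells in the core. The second is the clonal share diluted by non-tumor DNA in plasma. The two dilution factors are different quantities, and each varies between patients.

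A low CCC can therefore arise with no biological discordance at all. Sections 1.2 and 6.3.5 invite the reader to interpret tissue-plasma differences as heterogeneity, so dilution could be reported as a finding about metastatic sites.

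**Working it through.** **Plan's own figure.** There is none to reproduce. The documents give no expected kappa or CCC and no precision target, and 12.2 sets n = 40 by external constraints.

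**Inputs from the documents.** n = 40 (12.2). ESR1 mutation detectable in 25% (6.3.5), so 0.25 × 40 = 10 mutant patients expected. Biopsy optional (7.1).

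**Assumed inputs (the documents give none).** Clonal share c uniform on 0.2-1 and identical in both specimens. Biopsy purity P uniform on 30-80%. Plasma tumor fraction F log-normal with log SD 1, capped at 80%, median 2-30%. Heterozygous mutation and perfect detection. Then tissue frequency = cP/2 and plasma frequency = cF/2, so true clonal agreement is perfect.

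**Step 1: closed form.** CCC = 2·cov / (var₁ + var₂ + (mean difference)²). If plasma is exactly b times tissue (Pearson correlation 1) and tissue has coefficient of variation CV, then

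CCC = 2b·CV² / [(1 + b²)·CV² + (1 − b)²].

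- b = 0.1, CV = 0.5: 0.05 / (0.2525 + 0.81) = 0.047.
- b = 0.5, CV = 1: 1 / (1.25 + 0.25) = 0.667.
- b = 0.8, CV = 1: 1.6 / (1.64 + 0.04) = 0.952.

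If 75% of pairs are wild-type and entered as zeros, CV² becomes (1 + CV²)/0.25 − 1. For CV = 0.5 that is 4, and b = 0.1 gives 0.8 / (4.04 + 0.81) = 0.165.

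**Step 2: simulation under the assumptions above.**

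| Median plasma tumor fraction | CCC, double-positive pairs | CCC, 75% wild-type pairs as zeros |
|---|---|---|
| 2% | 0.02 | 0.09 |
| 5% | 0.04 | 0.22 |
| 10% | 0.10 | 0.40 |
| 20% | 0.21 | 0.62 |
| 30% | 0.31 | 0.73 |

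The right-hand column is higher because the zeros agree, not because the clones do. At a 10% median, drawing the two clonal shares independently still gives 0.34, against 0.40 when they are identical.

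**Step 3: simple repairs.** Over the same 2-30% range among double-positive pairs, a log scale gives 0.03-0.23, and removing the mean shift gives 0.08-0.37. Neither restores a value near 1, because the dilution varies between patients as well as shifting the mean.

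**Step 4: a second set of assumptions.** With every mutation fully clonal (c = 1) and purity and tumor fraction independent, the CCC among mutant pairs is about 0, even when mean purity and mean tumor fraction are both 0.6. With wild-type zeros at mean purity 0.6, it is 0.24, 0.67 and 0.93 at mean tumor fractions of 0.10, 0.30 and 0.60.

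**Step 5: the primary measure on agreeing patients.** With 10 both positive and 30 both negative, observed agreement is 1 and chance agreement is (10·10 + 30·30)/1600 = 0.625. Kappa = (1 − 0.625)/(1 − 0.625) = 1, whatever the dilution.

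**Step 6: what normalisation does.** Divide the ESR1 frequency by that of a fully clonal heterozygous alteration found in the same specimen. Tissue gives (cP/2)/(P/2) = c and plasma gives (cF/2)/(F/2) = c. The dilution cancels, so the CCC then measures agreement in clonal share. This holds only as far as the reference alteration really is clonal and of comparable copy number.

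**The case against.** The strongest case for the plan is that the objective concerns status, and 12.1 judges status mainly by presence/absence with a cluster-adjusted kappa. That stands. A reader might infer that secondary objective 3 fails, or that perfect clonal agreement would be reported as poor concordance. The documents do not support either reading: on the same perfectly agreeing patients the primary measure reports full agreement. Dilution reaches kappa only if it prevents detection in one specimen.

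Three further points also stand.

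- Section 12.1 does not say that allele frequency is analysed raw. That is inferred from its silence and from the Figure 3 definition.
- The size of the effect rests on purity and plasma fractions that the documents do not give, and the CCC reaches 0.93 in one scenario.
- This is a 40-patient exploratory study with no CCC threshold or decision rule, and 6.3.5 already expects plasma and biopsy detection to differ.

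The remedy also has limits. Sections 6.2 and 7.1 assign the panel sequencing to a biopsy core. Plasma NGS is planned in 7.2, but 11.1 words it as an alternative or addition to ddPCR and 6.3.5 calls it exploratory, so a matched plasma reference is not assured.

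None of this makes the unnormalised CCC interpretable. The high values come from wild-type zeros or nearly equal dilution. Neither tells the reader whether the clones agree.

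**Conclusion.** The point holds as a minor specification fault in the additional continuous analysis of 12.1. On the scale the documents supply, the CCC cannot separate dilution from the heterogeneity that 6.3.5 asks about. With identical clones it is about 0.02-0.31 among double-positive pairs, or about 0.09-0.73 with 75% wild-type zeros. The plan does not say which population applies. Those ranges depend on the assumed purity (30-80%), plasma tumor fraction (median 2-30%, log SD 1) and clonal share (0.2-1). The mechanism itself needs only that the two dilution factors differ and vary between patients. The primary presence/absence analysis is not in question.

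**What to change.** In 12.1, keep the cluster-adjusted kappa as the primary concordance measure and change the continuous part as follows.

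- State that a CCC on unnormalised allele frequency will not be used as a measure of tissue-plasma agreement or as evidence of heterogeneity.
- Restrict the continuous comparison to pairs positive for the same ESR1 variant in both specimens.
- For those pairs, report Spearman correlation and the tissue:plasma ratio, labelled as association. Say that a low Spearman value is not discordance either: under the same perfect-agreement assumptions it is only about 0.33-0.37.
- Where tissue and plasma NGS both exist and share a clonal alteration, apply the CCC to ESR1 allele frequency divided by that alteration's allele frequency, as an exploratory analysis.

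The cost is SAP wording and a small amount of analysis on data largely already planned. The downside is numbers: about 10 of 40 patients are expected to be mutant, biopsy is optional and plasma NGS is not assured. Few pairs will qualify and the normalised result will be imprecise.
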